### 5.2 Number of Participants

Up to 70 participants to be screened, with the aim to enrol up to 66 participants and with a view to achieve a cohort (participants completing the study as per protocol) sample size of 60 made up of approximately 20 in each of the low (near addition +0.75D to +1.25D), medium (near addition +1.50D and +1.75D) or high (near addition+2.00D to +2.50D) spectacle additions groups. Therefore 66 participants will be enrolled to account for drop out based upon a potential 10% drop out rate, has been determined to be optimal, balancing the need for sufficient discrimination and limiting inconvenience to participants by not inflating the study sample (see section 7.1).

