## 1 OVERALL SYNOPSIS

Study Sponsor	The Sponsor for this investigation will be CooperVision International Limited (CVIL) [name]. The sponsor contact will be [name].
Title of Study	Refitting Biofinity multifocal contact lens wearer with MyDay multifocal contact lenses.
Protocol Number	EX-MKTG-155 ID23-62
Type of study	The study will be conducted following an interventional, prospective, open label, sequential study design.
Study Population	Required: 60 completed participants as per protocol (cohort) with a minimum of 66 to be enrolled. Planned: Up to 70 screened, with the aim of enrolling 66 participants.
Duration of study treatment	14 (-0/+3) days of daily disposable, daily contact lens wear per study contact lens type.
Inclusion Criteria	
In order to be enrolled, each participant shall meet the following criteria:
 
 
i. Age 40 years and older;
 
ii. Current multifocal contact lens wearer (other than MyDay® multifocal but can include Biofinity® multifocal);
 
iii. Spectacle refraction: Distance: Sphere: -6.00D to + 4.00D Astigmatism: 0.00D to -0.75D Near Addition: +0.75D to +2.50D
 
iv. Best corrected visual acuity of at least 20/25 in each eye.
 
 
The prospective participants will be given a Participant Information Sheet to read and an Informed Consent Form to sign prior to any evaluation.

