## 7 SAMPLE SIZE DETERMINATION AND STATISTICAL ANALYSIS

### 7.1 Sample Size Determination

Sample size calculations took into consideration that the two co-primary endpoints to assess contact lens handling, inserting and removal, will be both required to be met at the completion of the study to demonstrate the study hypothesis. Accordingly non-inferiority testing was carried out considering a power of 90% in order to achieve a final power of 80% to test simultaneously the two primary endpoints. No adjustment is required for  $\alpha$ .

The results of a previous study involving similar population which measured contact lens handling (0-100 points visual analogue scale) achieved a standard deviation of the difference between two study contact lenses of 9.6 and 14.7 for insertion and removal respectively [1]. To demonstrate non-inferiority at both insertion and removal, considering a margin of non-inferiority of -7.00 and assuming no difference between test and control, for a one-sided paired t-test with  $\alpha = 2.5\%$  and  $\beta = 10\%$ , 49 participants are required to complete the study as per the protocol.

The reference study being conducted in the USA and involving a slightly different protocol (masked vs. open label) and considering that to be representative of the full range of presbyopes with similar number of young emergent, established and older advanced presbyopes with possible different levels of dexterity, the aim is to achieve a per protocol total population of 60 participants made up of approximately 20 in each of emergent low addition presbyopes (near addition +0.75D to +1.25D), established medium addition presbyopes (near addition +1.50D and +1.75D) and advanced high addition presbyopes (near addition +2.00D to +2.50D).

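### At the plan's own 10% drop-out, 66 enrolled gives 59.4 completers rather than 60, and 66 is a floor in the synopsis but a ceiling in section 5.2 (minor)

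*Combined protocol and SAP*

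**What the plan says.** The combined protocol and SAP gives the number of participants in three places.

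- **Synopsis, Study Population:** "Required: 60 completed participants as per protocol (cohort) with a minimum of 66 to be enrolled". The next sentence is softer: "Planned: Up to 70 screened, with the aim of enrolling 66 participants".
- **Section 5.2:** "Up to 70 participants to be screened, with the aim to enrol up to 66 participants". It names a per-protocol cohort of 60, about 20 in each near-addition group, and then concludes: "Therefore 66 participants will be enrolled to account for drop out based upon a potential 10% drop out rate, has been determined to be optimal".
- **Section 7.1:** the power calculation leads to the statement that "49 participants are required to complete the study as per the protocol". The number is then raised because the reference study differed in country and masking, and to cover the range of presbyopes: "the aim is to achieve a per protocol total population of 60 participants made up of approximately 20 in each".

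Section 5.4 lists the reasons for withdrawal and does not mention replacement. Nothing else in the available text states a replacement rule.

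**The concern.** There are two separate problems.

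The first is arithmetic. Section 5.2 presents 66 as the number that leaves 60 after a 10% loss. Adding 10% to the completer target does not do that, because the 10% is lost from the larger enrolled number. The stated enrolment therefore falls just short of the stated cohort on the plan's own assumption.

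The second is consistency. In the synopsis 66 is a floor; in section 5.2 it is a ceiling. The two agree only if exactly 66 are enrolled. If a seventh participant is lost, 60 completers can be reached only by enrolling a 67th. The synopsis minimum leaves room for that and the section 5.2 maximum does not.

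What is at stake is a clear and correct statement of trial size. A reader checking the report against the plan would find a cohort labelled as required that the plan had only about an even chance of reaching, and two enrolment limits that cannot both be applied.

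**Working it through.** **Inputs.** Target completers 60 (synopsis, 5.2, 7.1). Drop-out 10% (5.2). Enrolment 66 and screening limit 70 (synopsis, 5.2). Completers needed for the test 49; SD of the paired difference 9.6 for insertion and 14.7 for removal; margin -7.00; true difference 0; one-sided alpha 2.5%; power 90% per endpoint for 80% jointly (7.1).

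**1. Reproducing 66.** 60 x (1 + 0.10) = 66. This matches the plan exactly and shows how the figure was obtained.

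**2. What 66 delivers.** Expected completers = 66 x (1 - 0.10) = 59.4, which is 0.6 below 60.

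**3. Loss that 66 can absorb.** (66 - 60)/66 = 6/66 = 9.1%.

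**4. Enrolment consistent with 60 at 10%.** 60/(1 - 0.10) = 66.67, rounded up to 67. That is one more than stated and within the 70 to be screened.

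**5. Chance of at least 60 completers.** With N enrolled and each participant completing independently with probability 0.90, the number completing is Binomial(N, 0.90).

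| Enrolled | Expected completers | P(at least 60 complete) |
|---|---|---|
| 66 | 59.4 | 50.6% |
| 67 | 60.3 | 64.6% |
| 70 | 63.0 | 91.3% |

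The last row would require every person screened to be enrolled, so it is an upper bound.

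**6. Does the shortfall reach the primary test?** First the plan's 49. For a paired non-inferiority t-test, power = 1 - F(t(0.975, n-1)), where F is the noncentral t distribution with n-1 degrees of freedom and noncentrality 7 x sqrt(n)/SD. For removal (SD 14.7) the smallest n with at least 90% power is 49, with power 90.4%; the normal approximation gives 47. For insertion (SD 9.6) it is 22. The plan's 49 is reproduced.

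At the sizes in question:

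| Completers | Power, removal | Power, insertion | Product |
|---|---|---|---|
| 49 | 90.4% | 99.9% | 90.3% |
| 59 | 94.9% | 99.98% | 94.9% |
| 60 | 95.2% | 99.98% | 95.2% |

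Falling from 60 to 59 costs about 0.3 percentage points. With 66 enrolled and 10% loss, P(at least 49 complete) = 99.99%. Completers would drop below 49 only if more than 66 - 49 = 17 were lost, that is, more than 17/66 = 25.8%.

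**7. Floor against ceiling.** Up to six losses from 66 leave at least 60, and the two wordings do not collide. With seven losses, 66 - 7 = 59. Reaching 60 then needs a 67th participant, which is compatible with a minimum of 66 and incompatible with a maximum of 66.

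**The case against.** The strongest reply is that this is immaterial. The gap is 0.6 of a participant, the 10% is itself only a potential rate, and 60 is a deliberate cushion above the 49 that the test needs. The word required appears only in the synopsis; sections 5.2 and 7.1 treat 60 as something aimed for. Both the synopsis and section 5.2 also speak of 66 as an aim, so a reader could take them to mean the same thing. Most of this stands, and it is why the point is minor. It does not make 66 x 0.90 equal 60, and it does not reconcile a minimum with a maximum.

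Three stronger readings are tempting and are not supported.

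- **That the sections conflict on replacing leavers.** The available text has no replacement rule in either direction. A minimum of 66 leaves room for further enrolment but instructs nobody to replace a leaver; a maximum of 66 limits enrolment and says nothing about leavers. The documents are silent here, not contradictory.
- **That the near-addition groups are likely to fall short.** The plan asks for approximately 20 per group, so 20 is not a hard threshold. It gives no enrolment number per group, and the model in section 7.2 has no near-addition factor. A probability of missing 20 would rest on a threshold and a split that the plan does not contain.
- **That losses will exceed 10% because Visit 2 fit failures and protocol deviations come on top.** Section 5.2 uses the 10% to get from 66 enrolled to the per-protocol cohort, so it can be read as already covering these losses.

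**Conclusion.** The point holds as a minor error in a stated figure plus an inconsistency between two sections. On the plan's own 10%, 66 enrolled gives 59.4 completers, one enrolment short of the 67 that the same assumption implies, with about a 51% chance of reaching 60. The synopsis and section 5.2 cannot both govern once more than six participants are lost.

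The primary analysis is not threatened: 49 completers are all but certain at 10% loss, and power for removal is about 95% with 59 or 60.

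The probabilities assume independent losses at exactly 10%. The power figures assume the SDs, margin and zero true difference of section 7.1, with the paired t-test used there. The product of powers assumes independent endpoints; positive correlation would raise joint power, at most to the removal figure. A reader should not infer from this that the trial is underpowered or that the plan contradicts itself on replacement.

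**What to change.** Change the wording in the synopsis (Study Population) and in section 5.2 so that both:

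- state that 66 enrolled yields about 59 per-protocol completers at 10% loss, or equivalently that it tolerates a loss of 9.1%;
- describe 60 as a target and 49 as the number the primary test needs, in line with section 7.1;
- use one enrolment statement, making clear whether 66 is a floor, a target or a ceiling, within the existing limit of 70 screened.

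If the sponsor prefers to keep 60 as a firm requirement at 10% loss, the matching enrolment figure is 67, which still fits within 70 screened. A sentence on whether leavers are replaced would be a useful addition, but its absence is missing detail rather than an error.

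The main change costs wording in two places. It adds no participants and leaves the margin, the test and the 49 unchanged. The only downside is a slightly less favourable stated completer figure.

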### 5.3 Inclusion and Exclusion Criteria

#### 5.3.1 INCLUSION CRITERIA

In order to be enrolled, each participant shall meet the following criteria:

- i. Age 40 years and older
- ii. Current multifocal contact lens wearer (other than MyDay® multifocal but can include Biofinity® multifocal);
- iii. Spectacle refraction:

Distance:	Sphere: -6.00D to + 4.00D
Astigmatism:	0.00D to -0.75D
Near Addition:	Low +0.75D to +1.25D
	Medium +1.50D and +1.75D
	High +2.00D to +2.50D

- iv. Best corrected visual acuity of at least 20/25 in each eye.

The prospective participants will be given a Participant Information Sheet to read and an Informed Consent Form to sign prior to any evaluation.

### 5.3.2 EXCLUSION CRITERIA

To be eligible as a participant, each candidate shall be free of any ocular or medical condition that may affect the results of this study.

The following are specific criteria that exclude a candidate from enrolment in this study:

- i. Acute and subacute inflammation or infection of the anterior chamber of the eye.
- ii. Any eye disease, injury or abnormality that affects the cornea, conjunctiva or eyelids that would contraindicate contact lens wear;
- iii. Corneal hypoesthesia (reduced corneal sensitivity), if not aphakic
- iv. Severe insufficiency of lacrimal secretion (dry eyes).
- v. Any systemic disease that may affect the eye or may be exaggerated by wearing contact lenses (e.g. acne and eczema).
- vi. Allergic reactions of ocular surfaces or adnexa that may be induced or exaggerated by wearing contact lenses or use of contact lens solutions
- vii. Any active corneal infection (bacterial, fungal, protozoal or viral).
- viii. Newly prescribed (within the past 30 days) use of some systemic medications (such as antihistamines, decongestants, diuretics, muscle relaxants, tranquilizers, stimulants, anti-depressants, anti-psychotics, oral contraceptives) or new prescription eyedrops which is not rewetting/lubricating eyedrops for which contact lens wear could be contraindicated as determined by the investigator;
- ix. Monocular participants (only one eye with functional vision) or participants fit with only one contact lens;
- x. Subjects with slit lamp findings greater than grade 1 (e.g. edema, infiltrates, corneal neovascularization, corneal staining, tarsal abnormalities, conjunctival, anterior segment inflammation) as per ISO 11980, any previous history or signs of a contact lens related corneal inflammatory event (past corneal ulcers), or any other ocular abnormality that may contraindicate contact lens wear at the enrolment visit;
- xi. History of corneal refractive surgery
- xii. Enrolment of the family members of the investigator, family members of the investigator's staff, or individuals living in the households of these individuals.
- xiii. Current wearer of the test contact lens, MyDay® Multifocal.

### 5.4 Premature Withdrawal

A participant will be withdrawn from the investigation before completion if:

- i. The participant withdraws his/her consent to be included in the trial;
- ii. An adverse event takes place that is considered by the participant or the investigator to warrant withdrawal;
- iii. Any event that leads the investigator to believe that it is not in the best interest for the participant to continue in the study;

- iv. The study is prematurely terminated by the principal investigator, local research ethics committee or the Sponsor;
- v. The participant is lost to follow-up;
- vi. The participant no longer meets the eligibility criteria;
- vii. The participant dies.

### 5.5 *Informed Consent*

Each participant will give written consent according to local requirements after the nature of the study has been fully explained. Informed consent will be obtained by a delegated investigator that is GCP trained. The consent form will be signed before performance of any study-related activity. The consent form will have received approval by both the Sponsor and by the reviewing IEC before its use. The informed consent will be in accordance with principles that originated in the Declaration of Helsinki, current ICH and GCP guidelines, applicable regulatory requirements, and sponsor policy. Should a participant indicate on their consent form that they would like their GP to be notified of their participation in the research, then a letter will be sent to the GP.

Before entry into the study, the investigator or an authorised member of the investigational staff will explain to potential participant the aims, methods, reasonably anticipated benefits, and potential hazards of the study, and any discomfort it may entail. The potential participant will be informed that his/her participation is voluntary and that he/she may withdraw consent to participate at any time. The participant will be informed that choosing not to participate will not affect the care the participant will receive. Finally, the potential participant will be told that if needed his/her records may be accessed by health authorities and authorized sponsor staff without violating his/her confidentiality, to the extent permitted by the applicable law(s) or regulations.

The participant will be given sufficient time to read the participant information sheet and the informed consent form [REDACTED] and will have the opportunity to ask questions. If he/she requires additional time, the participant will be able to sign the consent on a future date and the enrolment visit will be re-scheduled accordingly; no research related measurement will be carried out before the potential participant has signed the informed consent.

After this explanation and before entry into the study, consent will be appropriately recorded by means of the participants' dated signature and counter signature of the member of the research team taking consent of two originals. After having obtained the consent, a copy of the participant information sheet and of the signed informed consent form will be given to the participant; the other signed copy of the informed consent will be kept in the study file.

## 6 STUDY DESIGN & PROCEDURES

### 6.1 *Experimental Design*

The study will be conducted following an interventional, prospective, open label, sequential study design.

The design has been developed to represent the clinical situation to be tested, that is the refitting of successful Biofinity® multifocal contact lens wearers with MyDay® multifocal contact lenses as per the following routine:

- i. Participants will be first fitted with Biofinity® multifocal contact lenses which they will wear for two weeks on a daily disposable wearing modality;
- ii. At the completion of the two weeks of wear the participants will be refitted with MyDay® multifocal contact lenses that they will wear for two weeks on a daily disposable wearing modality.

The participants will attend the clinic for three study visits. The participants will not take part in any concomitant investigation of any type or take concomitant medications not allowed by the exclusion criteria.

## 6.2 Experimental Routine

### Visit 1 – Screening /Enrolment / Fitting & Dispensing Biofinity® Multifocal Contact Lens

A prospective participant will attend the clinic for the first visit to initially obtain informed consent and evaluate the suitability to take part in the investigation. The potential participant will be asked to attend the clinic wearing spectacles and not have worn contact lenses that day. After informed consent has been given, the investigator will review the participant's medical history, ocular history [REDACTED] demographics and habitual contact lens wear history. A series of routine optometric assessments and tests will be conducted to determine the participant's prescription and evaluate the participant's ocular health.

Once it has been verified that the prospective participant meets the inclusion/exclusion criteria Biofinity® multifocal contact lenses will be inserted and worn for 10 minutes at which time the contact lens fit and vision will be assessed; [REDACTED]. If this is not achieved the participant will be discharged from the study; however, if a suitable fit is achieved the participant will then be instructed in the use of the contact lenses which will be dispensed to wear until Visit 2 as the main vision correction, aiming for at least 8 hours of wear a day for at least 5 days a week.

### Visit 2 – Biofinity® Multifocal Contact Lens Follow-up & MyDay® Multifocal Contact Lens Fitting and Dispensing visit (14 ± 3 days after visit 1)

The participant will return for the second study visit after having worn the first study contact lenses for 14 ± 3 days. The participant will attend the visit wearing Biofinity® multifocal contact lenses, having worn the contact lenses for a minimum of three hours prior to the appointment.

The participant's medical, ocular, contact lens wearing history and concomitant treatments will once again be reviewed. [REDACTED]

At the completion of the ocular integrity check the MyDay® Multifocal contact lenses will be inserted and worn for 10 minutes at which time the contact lens fit and vision will be assessed; [REDACTED]. If this is not achieved the participant will be discharged from the study; however, if a suitable fit is achieved the participant will then be instructed in the use of the contact lenses which will be dispensed to wear until Visit 3 as the main vision correction, aiming for at least 8 hours of wear a day for at least 5 days a week.

### Visit 3 –MyDay® Multifocal Contact Lens Follow-up & Discharge Visit (14 ± 3 days after Visit 2).

The participant will return for the third study visit after having worn the second study contact lenses for 14 ± 3 days. The participant will attend the visit wearing MyDay® multifocal contact lenses contact lenses, having worn the contact lenses for a minimum of three hours prior to the appointment.

The participant's medical, ocular, contact lens wearing history and concomitant treatments will once again be reviewed. [REDACTED]

[REDACTED] Then the MyDay® Multifocal contact lenses contact lenses will be removed.

[REDACTED] the participant will be discharged from the study.

### 6.3 End of Study

The end of the study clinical phase is at the discharge of the last participant from the study. The overall completion of the study is when the clinical study reports, EC report and ISCRTN result posting have been completed.

### 6.4 Participant Instruction

The participant will be instructed to wear the study contact lenses daily for  $14 \pm 3$  days, remove the contact lenses at night (prior to sleep), discard them and use a new identical pair of contact lenses the following day.

The participant will be advised on normal or adaptive symptoms related to contact lens wear. [REDACTED]

[REDACTED] These are not reported as adverse events unless in the investigator's opinion they are unexpected in nature, severity or have a high rate of occurrence.

The participant will be instructed to follow standard recommendations provided to contact lens wearers:

- i. Avoid rubbing the eyes, always wash hands prior to touching the eyes or handling the contact lenses, avoid being in a dusty environment and to use sunglasses when outdoors.
- ii. Exercise care while washing the face with tap water; avoid splashing tap water into the eyes.
- iii. Do not swim with contact lenses whenever possible.
- iv. Immediately contact the investigator and schedule to return to clinic for a check-up within 24 hours if the eyes become red, irritated or painful.

The participant will be provided with instruction sheets [REDACTED]

A participant using re-wetting eyedrops in combination with his/her habitual contact lenses will be able to continue to do so during the study.

### 6.5 Procedures

#### 6.5.1 EFFICACY PROCEDURES

The primary efficacy procedures will be the rating of contact lens handling combining ease of insertion and ease of removal both recorded on 100-point visual analog scales.

The secondary efficacy procedure will be the measurement of high luminance [REDACTED] high contrast (> 90%) logMAR visual acuity at distance [REDACTED], intermediate [REDACTED] and near [REDACTED] using OTG-i Vision Suite.

[REDACTED]  
[REDACTED]  
[REDACTED]  
[REDACTED]  
[REDACTED]

- i. [REDACTED]
- [REDACTED]
- [REDACTED]
- [REDACTED].

